4.2. Medical History

Medical history will be coded using the Medical Dictionary for Regulatory Activities (MedDRA®).

Medical history will include the following:

- Prior and current symptoms related to COVID-19
- Child-bearing potential/Menopausal history in women

4.3. Prior / Concomitant Medications or Procedures

Medications/Procedures will be recorded from the day of informed consent until the final study visit. Medications will be coded using the WHO Drug Dictionary (WHODD). Patients will be counted once in all ATC categories linked to the medication.

Prior medications/procedures are: medications taken or procedures performed prior to administration of the study drug.

Concomitant medications/procedures are: medications taken or procedures performed following the first dose of study drug through the final study visit. This includes medications that were started before the study and are ongoing during the study

A targeted list of following medications are expected to be recorded by the sites in the CRFs.

- Putative COVID-19 treatments (e.g., remdesivir, convalescent serum, IVIG, IL-6 receptor inhibitors [e.g., sarilumab, tocilizumab], JAK inhibitors [e.g., baricitinib], ivermectin)
- Antipyretics (e.g., aspirin, acetaminophen, ibuprofen)
- Anticoagulants (e.g., enoxaparin, warfarin, rivaroxaban)
- Immunosuppressants (e.g., cyclosporine A, steroids)
- Interferon beta
- Theophylline
- Antiepileptics (e.g., carbamazepine, divalproex, phenytoin)
- Antiarrhythmics (e.g., digoxin, disopyramide, procainamide)
- Antivirals, antibacterial, and antifungals
- Antiparasitics (chloroquine or hydroxychloroquine)
- Angiotensin receptor blockers (e.g., losartan, valsartan)
- Angiotensin converting enzyme inhibitors (e.g., benazepril, lisinopril)

Prior/Concomitant medications of interest for COVID-19: medications will be adjudicated in blinded manner by medical directors before database lock.

4.4. Rescue Medication/or Prohibited Medication During Study

Patients may receive rescue therapy for the treatment of COVID-19 per local standard-of-care. Rescue treatment(s) will not be provided as part of the study.

Patients are not permitted to receive any medication specified in the exclusion criteria for study enrollment. Patients may otherwise continue their normal regimen of medications and procedures.

SARS-CoV-2 Vaccination. Current CDC guidance recommends deferral of SARS-CoV-2 vaccination for at least 90 days after administration of passive antibody treatment (eg, REGN10933+REGN10987) (CDC, 2020):

Based on the estimated half-life of such therapies as well as evidence suggesting that reinfection is uncommon in the 90 days after initial infection, vaccination should be deferred for at least 90 days, as a precautionary measure until additional information becomes available, to avoid interference of the antibody treatment with vaccine-induced immune responses.

4.5. Efficacy Endpoints

4.5.1. Primary Endpoints

4.5.1.1. Primary Virologic Efficacy Endpoint

The **primary** virologic endpoint is time-weighted average change from baseline viral load in NP sample through day 7, as measured by quantitative reverse transcription polymerase chain reaction (RT-qPCR) in nasopharyngeal (NP) swab sample. The primary analysis will be performed for the Seronegative mFAS.

Time-weighted average of change from baseline in viral load in the NP swab samples will be calculated for each patient using the trapezoidal rule as the area under the curve for change from baseline at each time point divided by the time interval for the observation period (e.g., time interval will be 6 days for the observation period day 1 through day 7, or 10 days for observation period day 1 through day 11, etc.). This endpoint represents the reduction in average (mean) daily viral load from baseline.

For example, the time-weighted average (TWA) change from baseline in viral load in the NP swab samples till the last observation day t_k will be calculated using the formula

$$TWA_{[0-k]} = \left[\sum_{i=1}^k (t_i - t_{i-1}) * (D_i + D_{i-1})/2 \right] / (t_k - t_0)$$

Where

- k refers to the number of post-baseline assessments (e.g., $k=3$ for 3 post-baseline assessments through day 7, i.e., day 3, day 5, and day 7)
- D_i is the change from baseline in viral load value (\log_{10} copies/mL) obtained at time t_i , $D_0 = 0$
- t_i is the time(day) for which D_i is measured, such as $t_0 = 1$ (day) for baseline; and $\{t_i\} = 3, 5, 7$, for $i = 1$ to 3 where the postbaseline assessment is taken
- If the D_i is missing due to failed test or other reasons, only the time points with non-missing values will be included in the calculation. For example, we will calculate the TWA till day 7. Suppose the scheduled assessment result is missing at day 5 due to a failed test but non-missing at day 3 and day 7, then

$$TWA_{[0-3]} = [(t_1 - t_0) * (D_1 + D_0)/2 + (t_3 - t_1) * (D_3 + D_1)/2] / (t_3 - t_0)$$

Time-weighted average (TWA) change from baseline in viral load in any sample (nasopharyngeal, nasal or saliva) from day 1 through post-baseline day X is as described above. It represents the reduction in average (mean) daily viral load for the observation period of day 1 through day X.

Baseline is defined as the last non-missing viral load value (copies/mL) prior to the study drug infusion, unless specified otherwise. Patients with a missing baseline value will be excluded from the analysis.

Since viral load values (copies/mL) are expected to be highly skewed, these raw values will be transformed on \log_{10} scale to achieve symmetric distribution that can be approximated with normal distribution.

Viral load below the lower limit of detection (LLOD) of the assay (i.e., 299 copies/mL) will be imputed with 1 copy/mL, i.e., 0 \log_{10} copies/mL. Viral load values below the lower limit of quantification (LLOQ) of the assay (i.e., 714 copies/mL) but have positive results on the qualitative assay will be imputed as $LLOQ/2 = 357$ copies/mL. The upper limit of quantification of assay (ULOQ) is 71 million copies/mL (i.e., $\sim 7.85 \log_{10}$ copies/mL). Original assay test results above the upper limit of quantification ($>ULOQ$) of the assay will be replaced by results based on the diluted and reflexed testing results, when available. Otherwise, the ULOQ will be used in the analysis.

Change from baseline at day X in viral load in any sample is the post-baseline viral load at day X minus viral load at day 1. Change from baseline and TWA change from baseline will be derived based on \log_{10} copies/mL.

Percent change from baseline is the change from baseline divided by day 1 viral load. Percent change from baseline will be derived based on raw copies/mL.

4.5.1.2. Primary Clinical Efficacy Endpoint

The **primary** clinical endpoint is death or mechanical ventilation. It will be estimated by the proportion of patients who died or went on mechanical ventilation from day 6 through day 29 and from day 1 through day 29. The endpoint and populations are listed in [Table 3](#).

The proportion from day 6 to day X = (Total number of patients who died between day 6 to day X [days inclusive], or ever had ordinal scale = 2 (mechanical ventilation/ECMO) at any timepoint on or after day 6 through day X)/(Total number in the treatment group), where the following patients will be excluded from both numerator and denominator.

- Patients who died before day 6 or
- Patients who went on mechanical ventilation before day 6 or
- Patients who dropped out from study before day 6

The proportion from day 1 to day X = (Total number of patients who died on or before day X, or ever had ordinal scale = 2 (mechanical ventilation/ECMO) at any timepoint through day X)/(Total number in the treatment group)

Table 3: Primary Clinical Efficacy Endpoints and Populations

Endpoint	Timepoint	Population
Proportion of patients who died or went on mechanical ventilation (for cohort 1 and cohort 1A)	day 6 to day 29	1. High Viral Load mFAS 2. Seronegative mFAS, 3. mFAS
	day 1 to day 29	1. High Viral Load mFAS 2. Seronegative mFAS, 3. mFAS

Definitions of death or mechanical ventilation:

Death or mechanical ventilation is derived based on the patient vital status and the mechanical ventilation use recorded on Clinical status using an Ordinal Scale eCRF which is described in the following paragraphs. The patients who went on mechanical ventilation are those whose ordinal scale was 2.

Clinical status using Ordinal Scale: The ordinal scale provides an assessment of the clinical status of a patient (Peterson, 2017 [1]). The 7-point ordinal scale is as follows:

- 1 = Death
- 2 = Hospitalized, requiring invasive mechanical ventilation or extracorporeal membrane oxygenation (ECMO)
- 3 = Hospitalized, requiring non-invasive ventilation or high flow oxygen devices
- 4 = Hospitalized, requiring supplemental oxygen
- 5 = Hospitalized, not requiring supplemental oxygen – requiring ongoing medical care (COVID-19-related or otherwise)
- 6 = Hospitalized, not requiring supplemental oxygen – no longer requires ongoing medical care
- 7 = Not hospitalized

Clinical and oxygen status, vital status and hospitalization status will be collected and recorded on the CRFs as follows.

- Clinical and Oxygen Status – At Randomization CRF; Clinical and Oxygen Status – Pre-dose CRF; and Clinical and Oxygen Status – Post-dose visits CRF:
 - Use of supplemental oxygen: Yes/No
 - Type of Oxygen delivery device/ventilation, if using supplemental oxygen: Supplemental oxygen (not requiring high flow oxygen devices), Non-invasive ventilation or high flow oxygen devices,

Invasive mechanical ventilation,
Extracorporeal membrane oxygenation (ECMO)

- Vital status: Record vital status (dead or alive) of the day
- Hospitalization Status: Starting on day 2, record daily whether patient is hospitalized without requiring medical care or discharged.
- Hospital – ICU Admission and Discharge CRF: Record hospital discharge (if applicable) on the day of discharge
- Death Details CRF: Record any death (if applicable) on the day of death.

An ordinal scale score will be generated in the electronic database based on the records on clinical and oxygen status.

4.5.2. Secondary Endpoints

4.5.2.1. Secondary Virologic Efficacy Endpoints

The virologic efficacy endpoints are listed in [Table 4](#). Definitions of the endpoints are described in subsections below.

Table 4: Secondary Virologic Efficacy Endpoints and Populations

Endpoint	Timepoint	Population
Time-weighted average change from baseline viral load in NP sample	Through day 7	mFAS
Time-weighted average change from baseline viral load in NP sample	Through day 7	Baseline Viral load categories ($>10^5$, $>10^6$ copies/mL) mFAS
Time-weighted average change from baseline viral load in NP sample	Through day 11	Seronegative mFAS
Time-weighted average change from baseline viral load in NP sample	Through day 11	mFAS
Time-weighted average change from baseline viral load in NP sample	Through day 11	Baseline Viral load categories ($>10^5$, $>10^6$ copies/mL) mFAS
Time-weighted average change from baseline, change from baseline, and percent change from baseline in viral load in NP sample	Through each post-baseline timepoint until day 29	1. Seronegative mFAS, 2. Baseline Viral load categories ($>10^5$, $>10^6$ copies/mL) mFAS, 3. mFAS

The time-weighted average change from baseline, change from baseline, and percent change from baseline in viral load in NP sample are defined in Section [4.5.1.1](#).

4.5.2.2. Secondary Clinical Efficacy Endpoint

The secondary clinical efficacy endpoints and populations are defined in [Table 5](#). All clinical outcomes derived from the ordinal scale (Section [4.5.1.2](#)) will be based on data until day 29.

Definition of readmission

Readmission to hospital will also be based on what investigators report on *Hospital – ICU Admission and Discharge CRF*.

Table 5: Secondary Clinical Efficacy Endpoints and Populations

Endpoint	Timepoint	Population
Proportion of patients who went on mechanical ventilation (for cohort 1 and cohort 1A)	By day 29	1. High viral load mFAS, 2. Seronegative mFAS, 3. mFAS;
Proportion of patients who died	
 • day 6 to day 29 • day 1 to day 29 	
Proportion of patients who were discharged	By day 29	
Proportion of patients who died or were readmitted	All available follow-up data	
Cumulative incidence of Death (i.e. Overall Survival)	All available follow-up data	
Cumulative incidence of Mechanical Ventilation (for cohort 1 and cohort 1A)	All available follow-up data up to day 29	
Cumulative incidence of Death or Mechanical Ventilation (for cohort 1 and cohort 1A)	All available follow-up data up to day 29	
Time to Discharge	All available follow-up data	

4.5.2.3. Clinical Endpoints based on Proportions

Clinical endpoints based on proportions will be computed as numerator over denominator as given in [Table 6](#).

Table 6: Secondary Clinical Endpoints based on Proportions of Patients with Outcome

Number	Endpoint	Timepoint	Numerator	Denominator
1.	Died	day 6 to day X	Total number of patients who died after day 5 and on or before day X (death data will be captured from any CRF in the study)	Number of patients in the treatment group excluding patients who died or dropped out before day 6

		day 1 to day X	Total number of patients who died on or before day X (death data will be captured from any CRF in the study)	Number of patients in the treatment group
2.	Went on Mechanical Ventilation	Through day X	Number of patients who ever went on mechanical ventilation or ECMO (ordinal scale =2) through day X	Number of patients in the treatment group
3.	Discharge	Through day X	Number of patients who discharged through day X	Number of patients in the treatment group
4	Death or readmission	Through end of study	Number of patients who died or readmitted into hospital during the study	Number of patients in the treatment group

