9.1.3. Early Termination from the Study

Patients who are withdrawn from the study prior to day 29 will be asked to complete an early termination (ET) visit consisting of day 29 assessments and sample collections. In phase 1, patients withdrawn from the study after day 29 will be asked to complete an ET visit consisting of the EOS visit (day 169) assessments and sample collections. In phase 2, patients withdrawn from the study after day 29 will be asked to complete an ET phone visit consisting of the EOS visit (day 57) assessments.

All patients who are withdrawn from the study will be contacted by phone to obtain vital status. For patients in phase 1, this call will occur on day 169. For patients in phase 2, this will occur on day 57.

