2.4.1. Definition of Study Completion

For individual patients, study completion is defined as collection of vital status information on their projected EOS date. All measures will be taken to obtain vital status information on the projected EOS date, and all patients with recorded vital status information at projected EOS date will be considered study completers. The end of study is considered day 169 (for phase 1) or day 57 (for phase 2 and phase 3) (refer to Section 10 Schedule of Events).

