5.6.2.2. Descriptive Analysis of Secondary Clinical Efficacy Endpoints

All clinical endpoints based on proportions (defined in Section 4.5.2.3) will be analyzed using similar methods as for the primary clinical efficacy endpoint described in Section 5.6.1.2. The analysis will be performed for patients by baseline viral load ($\leq 10^6$ vs $> 10^6$ copies/mL) in the mFAS, by serostatus in the mFAS, and in overall mFAS.

All clinical endpoints based on time-to-event (defined in Section 4.5.2.4) will be estimated using the Kaplan-Meier method and comparisons between treatment groups will be made using the stratified log-rank test with the type of background standard-of-care as stratification factor. P-values will be compared with 0.05 (two-sided).

The log-rank “observed minus expected” statistic (and its variance) will be used to calculate the one-step estimate of the event rate ratio and confidence interval for each pairwise comparison versus placebo group (Peto 1977) [2].

As sensitivity analysis, the hazard ratio and its 95% CI will be estimated by the Cox proportional-hazards regression model with terms for treatment group, and type of background standard-of-care. P values from the stratified log-rank test will be reported. Hazard ratio (HR) < 1 will imply reduction of hazard of REGN10933+REGN10987 versus placebo. Estimates of median times along with 25th and 75th percentiles (if median and quartiles are reached) and associated two-sided 95% CI will be reported using the Kaplan-Meier method.

Landmark analysis starting from day 6 will be performed using similar Cox proportional-hazard model on the cumulative incidence of death or mechanical ventilation and cumulative incidence of death. The patients with corresponding events occurring before day 6 and patients who drop out early from study before day 6 will be excluded from the analysis (Dafni, U. 2011) [3]. The analysis will be performed for patients by baseline viral load ($\leq 10^6$ vs $> 10^6$ copies/mL) in mFAS (with baseline serostatus added to the stratified log-rank test and the Cox model as a factor), by serostatus in mFAS, and overall mFAS (with baseline serostatus added to the stratified log-rank test and the Cox model as a factor).

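### SAP Table 6 counts deaths of patients who withdrew before day 6 in the numerator of the day 6 to day X death proportion but removes those patients from the denominator

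*SAP*

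**What the plan says.** SAP 4.5.2.3, Table 6, row 1 (Died, day 6 to day X) gives the numerator as "Total number of patients who died after day 5 and on or before day X", with deaths taken from any CRF in the study. The denominator is "Number of patients in the treatment group excluding patients who died or dropped out before day 6". The companion day 1 to day X row uses the whole treatment group as denominator.

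SAP 4.5.1.2 defines the primary day 6-29 composite of death or mechanical ventilation with a list of patients, "where the following patients will be excluded from both numerator and denominator". The list includes "Patients who dropped out from study before day 6". The day 1-29 composite in the same section has no such exclusion.

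For the day-6 landmark Cox analyses of death and of the composite, SAP 5.6.2.2 says "patients who drop out early from study before day 6 will be excluded from the analysis".

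On follow-up after withdrawal, Protocol 9.1.3 says "All patients who are withdrawn from the study will be contacted by phone to obtain vital status", on day 57 for phase 2. SAP 2.4.1 says "All measures will be taken to obtain vital status information on the projected EOS date" and gives that date as day 57 for phases 2 and 3.

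**The concern.** A proportion needs a numerator drawn from its denominator. In Table 6 the exclusion of early dropouts is attached only to the denominator. Because vital status is sought after withdrawal and deaths from any CRF count, a death after early withdrawal can reach the numerator while the patient is missing below. Whenever that happens, the result is higher than under either consistent definition. It also disagrees with the landmark Cox analysis of death, which leaves the patient out altogether.

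There is a lesser issue for the primary day 6-29 composite, which occupies steps 2 to 4 of the testing hierarchy. It removes early dropouts from both sides, so the ratio is sound, but a known death after withdrawal is lost there and counted in steps 5 to 7 (day 1-29).

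**Working it through.** **Text check.** Take a dosed patient who withdraws on day 3 and dies on day 12, with the death recorded.

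| Analysis | Counted as an event | In the denominator or risk set |
|---|---|---|
| Primary composite, day 6-29 (SAP 4.5.1.2) | no | no |
| Died, day 6 to X (Table 6) | yes | no |
| Landmark Cox from day 6 (SAP 5.6.2.2) | no | no |
| Primary composite, day 1-29 (SAP 4.5.1.2) | yes | yes |
| Died, day 1 to X (Table 6) | yes | yes |

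Only the second row is internally inconsistent.

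**Size.** No figure stated in the plan depends on this rule, so there is nothing to reproduce, and neither document gives the number of dropouts before day 6. The following is illustration only.

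Example with assumed counts for one arm: 380 patients, 8 deaths before day 6, 10 withdrawals before day 6, 25 deaths on day 6-29 among those who stay and 2 among those who withdrew.

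- Table 6 as written: (25 + 2)/(380 - 8 - 10) = 27/362 = 7.46%
- Withdrawals out of both sides: 25/362 = 6.91%
- Withdrawals in both sides: 27/(380 - 8) = 27/372 = 7.26%

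Range. Let 2% die before day 6, w be the share withdrawing before day 6, R = 0.98 - w the share staying, p = 8% the day 6-29 mortality in stayers, and m that in early withdrawals. All of these are assumed.

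- Table 6 = (R×p + w×m)/R
- Out of both = p
- In both = (R×p + w×m)/(R + w)

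| w | m | Table 6 | Out of both | In both |
|---|---|---|---|---|
| 1% | 8% | 8.08% | 8.00% | 8.00% |
| 5% | 20% | 9.1% | 8.0% | 8.6% |
| 5% | 30% | 9.61% | 8.00% | 9.12% |

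If withdrawal differed by arm, say 2% on placebo and 5% on active with m = 20%, keeping everyone gives 8.61%/8.24% = 1.045 (before rounding the two rates), Table 6 gives 9.08%/8.42% = 1.08, and exclusion gives 1.00.

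**Deaths the primary composite might lose.** The overall mFAS size is not stated. It can be inferred from the 29.0% minimal significant relative reduction at a 13.1% placebo rate, two-sided 0.05 and 2:1 allocation (SAP 2.3). With p0 = 0.131 and p1 = 0.131 × 0.71 = 0.0930, the difference is 0.0380 and the pooled rate is (0.131 + 2 × 0.0930)/3 = 0.1057. Then n0 = 1.96² × 1.5 × 0.1057 × 0.8943/0.0380² ≈ 377 on placebo (using unrounded values), about 1132 in all. Known day 6-29 deaths removed would run from 1132 × 1% × 8% = 0.9 to 1132 × 5% × 20% = 11.3, again on assumed withdrawal and mortality.

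**The case against.** The strongest reply is that this is missing wording. SAP 4.5.1.2 applies the exclusion to both sides, SAP 5.6.2.2 analyses secondary proportions by methods similar to the primary, and the authors may have meant the same in Table 6. That is plausible, but Table 6 does not say so, and its instruction to take deaths from any CRF points the other way.

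A second reply is that dropping out is never defined, and that Protocol 6.1.6 and SAP 2.4.1 treat anyone with vital status recorded at the projected end of study as a completer. On that reading, a patient with known vital status is not a dropout and the mismatch largely disappears. However, none of the three places that exclude dropouts refers to the completer definition. The ambiguity is a reason to define the term.

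A reader might go further and infer that the primary day 6-29 test is invalid, or that the exclusion breaks the randomized comparison. The documents do not support that:

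- The primary ratio uses one set throughout.
- Any day-6 landmark already conditions on what happened after dosing, and the day 1-29 tests keep the full denominator.
- No withdrawal rate, and no difference between arms, is reported.
- Ventilation comes from the clinical status record and is not observed after withdrawal. Keeping early withdrawals in the primary composite would score unknown ventilation as a non-event under the missing-data rule in SAP 5.6.1.2, so inclusion is not plainly better there.

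Nor can one assume that every death after withdrawal is known and dated. Protocol 9.1.3 describes a call for vital status without mentioning a date of death, and names only phases 1 and 2. Phase 3 follows from the shared schedule and SAP 2.4.1. Patients who withdraw consent may be out of reach.

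**Conclusion.** Table 6 row 1 is wrong as written and should be corrected: its numerator can include patients who are not in its denominator. This rests on the literal text and needs no assumption about rates. The practical size is unknown because early dropout is not stated, and it is probably small; the percentages and risk ratios shown rest wholly on assumed withdrawal and mortality. The row is a descriptive secondary endpoint with nominal p-values (SAP 5.6.2), so no hierarchical test depends on it.

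The primary day 6-29 composite is internally consistent. Its limitation is that it can set aside known deaths after early withdrawal that the day 1-29 composite counts. That calls for a sensitivity analysis, not a new primary definition.

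**What to change.** 1. In Table 6 row 1, use one day-6 landmark set for numerator and denominator.
2. For the death-only day 6-29 proportion and the landmark Cox analysis of death, define that set as patients not known to have died before day 6. Keep early withdrawals whose vital status after day 5 is known, and exclude only those with no vital status after day 5. In the Cox analysis, censor only where follow-up is truly missing.
3. Leave the primary day 6-29 composite as it is. Add a sensitivity analysis that keeps early withdrawals with known vital status, and state that their later ventilation is unobserved.
4. Define dropping out, say how a death reported without a date is handled, and report by arm how many patients withdrew before day 6 and how many of those have known vital status.

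The cost is a few lines of SAP text and some programming before database lock; no new data are collected. One caution is that selecting on known vital status is itself a selection after randomization, and could favour deaths if they are ascertained more readily than survival. The counts in item 4 let a reader judge that.
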